4.1 Study Endpoints

Since our primary thesis is that GLASSIA will increase islet engraftment in the early perioperative period our primary endpoint for which the study is powered is a comparison of insulin independence rates of GLASSIA treated versus control patients at day 75 post transplant. We are fortunate to have permission to utilize data from the CIT-06 trial which will allow a large number of control patients. Since our proposed trial was directly derived from CIT-06 in terms of entry criteria, treatment regimen and post transplant monitoring except for treatment with GLASSIA and related mechanistic studies, these cohorts provide us a highly relevant comparator and allow us to enroll more GLASSIA treated patients than if a randomized trial. This increases the power of the trial making it likely that we will be able to detect differences between treated and control groups should GLASSIA exert the hypothesized benefit to engraftment.

For our primary mechanistic assessment to measure engrafted functional islet mass we will rely on the frequently sampled intravenous glucose tolerance test (FSIGT) from which an AUC for insulin secretion correlates with islet mass. Each of the 24 CIT-06 patients had this test performed at day 75. Of note, we had previously considered use of a glucose potentiated arginine stimulation test for this purpose. However, no CIT-06 patients had this test performed¹³¹⁻¹³².

Because the assessment of islet graft function is dependent on complex physiologic relationships between the graft and its recipient, no single test adequately addresses the metabolic impact of the transplant. Therefore, HbA1c and the number of episodes of severe hypoglycemia will be used as clinically relevant measures of islet graft function for secondary endpoints, and additional stimulatory tests of islet graft function utilizing MMTT, glucose, and the CPGCR will be used to assess secondary endpoints. Also, the effect of islet graft function on glycemic control (HbA1c), glycemic lability (MAGE and LI), hypoglycemia (Clarke and HYPO scores), glucose variability (CGMS®), cardiovascular impact, and renal impact will be assessed as additional secondary endpoints¹³²⁻¹³⁶. Each of these were collected in CIT-06 patients and will add to the robustness of our comparison of the metabolic outcome between GLASSIA treated and control CIT-06 subjects.

Study endpoints are listed relative to the islet transplant occurring on Day = 0. The timing of all assessments is provided in the Schedule of Events (Appendix 1). For logistical purposes, the day 75 time point is equivalent to the 3 month evaluation.

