In addition, increasing evidence suggests that blocking TNF- α in the early post-transplant period will diminish nonspecific islet β cell loss, maximize engraftment and functional survival of transplanted islets, and thus increase the proportion of islet allograft recipients who become insulin independent following single-donor islet allotransplantation. TNF- α is known to be cytotoxic to human islet β cells⁹⁵. In murine models, selective inhibition of TNF- α in the peritransplant period has promoted reversal of diabetes after marginal-mass islet isografts⁹⁶. Temporary etanercept administration has previously been studied in globally immunosuppressed kidney⁸⁹ and bone marrow transplant recipients^{87, 88}. In renal transplant recipients, etanercept was combined with depleting T cell antibodies (hOKT3y1 ala-ala or ATG). These studies demonstrated that etanercept is well tolerated and may limit the severity of the acute cytokine release syndrome associated with hOKT3y1 ala-ala and ATG administration.

Compared with the hOKT3y1 ala-ala trial²⁶, in which 4 of 6 single-donor islet recipients achieved and maintained insulin independence, the 8 recipients with sustained insulin independence in the ATG plus etanercept trial⁹² had a significantly higher acute c-peptide response to arginine (ACRArg) on days \geq 180 post-transplant: 1.07 ± 0.15 ng/mL (vs. 0.74 ± 0.21 ng/mL in the hOKT3y1 ala-ala trial²⁶; $p=0.028$). This improvement occurred despite transplantation of fewer islets: $7,271 \pm 1,035$ IEq/kg (vs. $10,302 \pm 2,594$ IEq/kg in the hOKT3y1 ala-ala trial; $p=0.01$). To facilitate comparison of the proportion of engrafted islets between studies, the ACRArg was corrected for implanted IEq/kg, and expressed as the engraftment index.

The success with a rabbit ATG based regimen is perhaps not unexpected in light of data confirming it to be highly efficacious in prevention and treatment of allogeneic rejection^{82-85, 97}. In many kidney series, 1-year rejection rates as low as 5% have been achieved using a brief course of rabbit ATG induction in low immunological risk patients. For this reason, it has become the preferred induction agent for kidney and kidney-pancreas transplant at many centers. It has also been applied with success for non-renal organs^{83, 98}.

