1.5.6 Procedures for Minimizing Risks

A number of features of the proposal have been designed to maximize the safety of subjects in the trial. Important selection criteria include avoidance of any medical condition that might significantly increase the risk related to islet transplantation. Importantly this includes selection of kidney recipients who have stable graft function and who are at a low risk for rejection of their graft. In addition, renal graft function in potential trial subjects has to be sufficient (CrCl of > 40 mL/min) so that it is unlikely that they will experience imminent graft failure and face the need for ongoing immunosuppression for an islet graft in the absence of a functioning kidney.

To ensure further that there is no detrimental impact on renal graft function, the maintenance immunosuppression regimen already in place for the renal graft will be continued without marked changes to benefit the islet transplant. This approach will avoid immunosuppressant drug changes that

could potentially precipitate renal allograft rejection.

In addition, the induction immunosuppression regimen based on rabbit ATG is well studied and has been demonstrated to have a favorable safety profile in solid organ transplantation. The islet preparation to be infused will be isolated from cadaveric donors thoroughly tested for transmissible infectious agents and will be free of recent high-risk behaviors. In addition, the islet product will be tested preinfusion to verify a suitable level of purity, viability, mass, and endotoxin.

Since gaining insulin independence is dependent on the recovery and infusion of a sufficient islet mass per recipient BW, the trial has been limited subjects < 100 kg in an attempt to maximize the likelihood that insulin independence will be achieved with one (or two) islet transplants. It is recognized that subjects ≥ 100 kg should benefit equally for this therapy should a sufficient islet mass be obtainable.

The informed consent process is carefully organized to minimize unrealistic expectations. We will also reject volunteer subjects who are so desperate as to be incapable of understanding and/or coping with the possibility of failure. We believe that our process leading to informed consent is purposefully organized so as to minimize psychological risk to the recipient.

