4.1.2 Secondary Endpoints

Key Secondary Endpoint

Insulin independence

- The proportion of GLASSIA treated versus control CIT-06 subjects who are insulin independent after 1 or more islet infusions at:
 - 1 year after the first islet infusion
 - 1 year after the last islet infusion
 - 2 years after the first islet infusion
 - 2 years after the last islet infusion

Other Secondary Endpoints

Insulin Utilization

- The proportion of GLASSIA treated versus control CIT-06 subjects who are insulin independent after 1 or more islet infusions at:
 - 1 year after the first islet infusion
 - 1 year after the last islet infusion
 - 2 years after the first islet infusion
 - 2 years after the last islet infusion
- Percent change from baseline insulin requirement comparing GLASSIA treated versus control CIT-06 subjects at Day 75, 1 year and 2 years following the first and last islet transplant(s)

Islet Mass

The relative functional engrafted islet mass comparing GLASSIA treated versus control CIT-06 subjects using FSIGT testing at:

- Day 75 after the first islet transplant
- 1 year after the first islet transplant
- 2 years after the first islet transplant
- Correlation of markers of early islet loss as assessed by the rapid release of thrombin-anti thrombin complexes (TAT), C3 and c-peptide, and insulin specific DNA with FSIGT and clinical markers of islet function (HbA1c, insulin independence rates, duration of islet function and insulin independence)
- The proportion of GLASSIA treated versus CIT-06 control subjects with both an HbA1c ≤ 6.5% AND an absence of severe hypoglycemic events:
 - From Day 28 to Day 365 after the first islet transplant
 - From Day 28 to Day 730 after the first islet transplant.
- The proportion of GLASSIA treated versus control subjects with both an HbA1c < 7.0% AND free of severe hypoglycemic events:
 - From Day 28 to Day 365 after the first islet transplant.
 - From Day 28 to Day 730 after the first islet transplant
- The proportion of GLASSIA treated versus control CIT-06 subjects A reduction in HbA1c of 1 point AND an absence of severe hypoglycemia from:
 - From Day 28 to Day 365 after the first islet transplant
 - From Day 28 to Day 730 after the first islet transplant
- Number of severe hypoglycemic events comparing GLASSIA treated versus control CIT-06

subjects at 1 year and 2 years following the *first* and *last* islet transplant(s)

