7.4 Islet Transplant and Study Treatment Visits

Blood group compatible and crossmatch negative subjects selected for islet transplantation will be invited to the study center upon determination of preliminary islet suitability based on count and quality. After preliminary testing detailed in Appendix 1, SOE (- 2 days relative to transplant), the subject will be admitted for induction therapy with rabbit ATG. This can be administered via central vein catheter, PICC line, or peripheral IV⁹⁸. A period of in vitro culture is considered essential to the protocol because of the use of rabbit ATG induction

Immunosuppression may cause a transient cytokine release associated with the initial doses. The period of in vitro culture will allow time for any cytokine release to dissipate after treatment of the subject with ATG and will also permit time for microbiological and potency assessment of the islet preparation prior to transplant.

Once islets have been examined at the end of the culture period but prior to final release testing, the pharmacy will compile the needed dose to allow the infusion to be completed within three hours of reconstitution. GLASSIA will be infused within three hours before the intended start of the islet infusion but after the final release criteria confirm islet suitability.

Following induction therapy, subjects will remain on a calcineurin-based maintenance immunosuppression regimen. This can consist of tacrolimus alone or in conjunction with sirolimus, mycophenolate mofetil, myfortic, or azathioprine; or cyclosporine in conjunction with sirolimus,

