10. STATISTICAL CONSIDERATIONS AND ANALYTICAL PLAN

10.1 Study Endpoint Assessment

10.1.1 Primary Endpoint

Since our primary thesis is that GLASSIA will increase islet engraftment in the early perioperative period our primary endpoint for which the study is powered is a mechanistic assessment of the functional islet mass early (day 75) post transplant. We will rely on the frequently sampled intravenous glucose tolerance test (FSIGT) from which an AUC for insulin secretion correlates with islet mass for our primary mechanistic assessment of functional islet mass. Data from the CIT06 trial, which performed this test on all patients at day 75, will serve as the control. Such controls increase the power of the trial making it likely that we will be able to detect differences between treated and control groups should GLASSIA exert the hypothesized benefit to engraftment.

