Most of the secondary endpoints are measured before transplant, at day 75 (A1c, MMT, FSIGT, MAGE, c-peptide and Beta score) and at one year post-initial transplant (HbA1c, fasting and 90 minute MMTT, c-peptide, glucose, and c-peptide glucose creatinine ratio, MAGE, HYPO, Clarke survey, and Beta score). We will compare these markers with those in the CIT-06 controls using student's t-test, nonparametric test (e.g., Mann-Whitney U test, Wilcoxon signed rank test), or chi-square test when appropriate. A pre-post analysis will be used for these variables. For continuous variables that are normally distributed or that can be transformed to a normal distribution, we will compute an appropriate estimate and 95% confidence interval for the mean change and a paired t-test for testing that the mean change is zero. If an appropriate normalizing transform cannot be identified then a signed-rank test will be used to test for a significant change. Similarly, a McNemar test will be used to test for a significant change for dichotomous outcome variables.

For those continuous secondary endpoints that are only observable after transplantation or for whom

change from baseline are not meaningful we will compute estimates of the mean and 95% confidence intervals. Similarly, for binary endpoints we will compute the observed rates and exact 95% confidence intervals. Levels of these markers will be compared with those in the CIT-06 controls using student's t-test or nonparametric test (e.g., Mann-Whitney U test) when appropriate.

Regression models for continuous longitudinal data (mixed models) will be used to describe the profiles of change over time for each of the response variables where measurements are repeated over time. Similar models will be used to model dichotomous variables over time.

Survival analysis models will be used to compare time to becoming insulin dependent and to identify risk factors through Kaplan-Meier estimates and Cox regression models.

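### The day-75 FSIGT comparison with CIT-06 takes no account of infused islet dose, so a dose difference between the cohorts could mimic or mask an AAT effect on engraftment.

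*Combined protocol and SAP*

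**What the plan says.** Section 4.1 sets out the mechanistic measure: "we will rely on the frequently sampled intravenous glucose tolerance test (FSIGT) from which an AUC for insulin secretion correlates with islet mass". Section 10.1.1 repeats it, describing an FSIGT "from which an AUC for insulin secretion correlates with islet mass for our primary mechanistic assessment of functional islet mass". In section 4.1.2 the endpoint reads "The relative functional engrafted islet mass comparing GLASSIA treated versus control CIT-06 subjects using FSIGT testing at" day 75, 1 year and 2 years after the first transplant. What the mass is relative to is not explained.

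The controls are external. Section 4.1 says of the FSIGT: "Each of the 24 CIT-06 patients had this test performed at day 75". Section 7.8.1 describes the study as open-label and non-randomized. For between-cohort comparisons, section 10.1.2 says "We will compare these markers with those in the CIT-06 controls using student's t-test, nonparametric test" or chi-square. The mixed models mentioned there describe change over time and name no dose term. The demographic summary in section 10.2.1 covers age, race, sex, weight and height.

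Sections 4 and 5.2.1 give the first-infusion dose a floor of 5,000 IEq/kg and no ceiling. Where section 1.1 argues that the cohorts are alike, it cites selection, manufacturing, management and follow-up, but not infused dose.

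Two background sections treat dose as a determinant of outcome. Section 1.4, comparing two earlier islet trials, reports that "the ACRArg was corrected for implanted IEq/kg, and expressed as the engraftment index". Section 1.5.6 begins a justification of the weight limit with "Since gaining insulin independence is dependent on the recovery and infusion of a sufficient islet mass per recipient BW".

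**The concern.** The primary thesis is that AAT raises engraftment. To a first approximation, the mass that survives to day 75 is the mass infused times the fraction that engrafts. AAT is meant to act on the fraction, while the AUC tracks the product. In a randomized trial the dose would balance on average. Here the comparator is an earlier trial, and the dose depends on donor yield and recipient weight, so nothing in the design equalises it.

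An unadjusted difference in AUC therefore mixes a treatment effect with any difference in dose. At stake is the comparison that the protocol calls its main mechanistic assessment, and which section 10.1.1 goes so far as to call the powered endpoint. Day-75 insulin independence depends on dose too, as section 1.5.6 acknowledges.

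**Working it through.** **The plan's own figures.** The documents give no FSIGT mean, SD, sample size or power. The stated 87% power in section 10.3.1 concerns insulin independence. It reproduces as an exact one-sample binomial (8 or more of 20, null 16.7%, true rate 50%: 86.8%), but it says nothing about the FSIGT comparison.

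**The protocol's example (section 1.4).** Arginine-stimulated c-peptide response was 1.07 versus 0.74 ng/mL, after 7,271 versus 10,302 IEq/kg.
- Uncorrected ratio: 1.07 / 0.74 = 1.45.
- Ratio per IEq/kg: (1.07 / 7,271) / (0.74 / 10,302) = 2.05.
- Dose ratio: 10,302 / 7,271 = 1.42, the factor by which the correction moves the contrast.

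The correction enlarges the difference here, because the better-responding cohort received fewer islets. The example shows that dose can move a cross-trial contrast materially. It does not show a false positive.

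**False-positive rate under a dose imbalance.** Inputs from the documents: 20 treated subjects and 24 controls. Assumptions: AUC proportional to dose, no AAT effect, CV of AUC 50% (range 40% to 60%), and a mean dose higher by a proportion d in the GLASSIA cohort. For a two-sample t-test with 42 degrees of freedom and critical value 2.018,

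ncp = (d / CV) / √(1/20 + 1/24) = (d / CV) / 0.3028.

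| Dose excess d | ncp at CV 50% | P(p < 0.05), CV 50% | Range, CV 60% to 40% |
|---|---|---|---|
| 5% | 0.33 | 6% | 6% to 7% |
| 10% | 0.66 | 10% | 8% to 13% |
| 15% | 0.99 | 16% | 13% to 23% |
| 20% | 1.32 | 25% | 19% to 36% |

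With d negative the same shift acts in the other direction and offsets a true benefit.

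**Check by simulation.** This used log AUC, a within-cohort dose CV of 20%, an AUC-per-dose CV of 40% to 80% and no AAT effect. A 10% excess gave 7% to 11% significant tests, and a 20% excess gave 13% to 28%. After division by IEq/kg the rate was about 5% throughout (4.7% to 5.2%).

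**Is dose a legitimate covariate?** For the first infusion, yes. Section 1.5.6 says islet mass is verified before infusion. Section 7.4 times the first GLASSIA infusion "after the final release criteria confirm islet suitability", so the drug cannot alter that dose. Later infusions differ. Up to three are allowed (section 4), and reinfusion depends on how the graft performs (section 7.6). Cumulative IEq/kg at 1 and 2 years is therefore a post-treatment quantity, and adjusting for it could remove part of a real effect.

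**The case against.** A reader might infer that the sponsor chose a raw AUC. The documents do not say so. The endpoint is called relative, and that might mean relative to dose or merely relative to control. The supported defect is an undefined endpoint with no stated normalisation, tested without adjustment.

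A reader might also infer that the AUC is the wrong measure. The primary objective (section 2.1) speaks of functional engrafted mass as an amount, which the AUC does address. Dose is a matter of comparability with an external control.

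Nor do the documents show that the cohorts differ in dose, or that a bias would favour AAT. CIT-06 doses are not given. Similar recipient selection and islet manufacturing (section 1.1) and standardized lot-release assays (section 1.3.2) make a large gap less likely, though they do not equalise IEq/kg. Bias in either direction is possible. The roughly 2-3% of islets placed in the auxiliary graft (section 5.2.1, with opt-out) slightly lowers the intraportal dose in this trial.

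Finally, the powered test is the one-sample binomial on insulin independence. Section 4.1.2 lists the FSIGT among the other secondary endpoints, section 10.1.2 promises qualifiers on secondary findings, and section 10.1.3 assigns engrafted mass descriptive analysis. This limits the consequence. It does not remove the gap, because sections 4.1 and 10.1.1 still rest the mechanistic claim on this comparison and no section accounts for dose.

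**Conclusion.** The point holds for the day-75 FSIGT comparison. It is planned without adjustment against a non-randomized control, with no stated normalisation for infused islets, although the protocol's own rationale makes that correction when comparing islet trials. A difference in first-infusion IEq/kg could mimic or mask an AAT effect.

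The size cannot be computed from the documents. On the stated assumptions (proportionality, CV 50%, no AAT effect) the two-sided 5% test would reject about 10%, 16% or 25% of the time for a 10%, 15% or 20% dose excess, and little above 5% for a 5% excess. Larger CVs lower these figures. This is a worthwhile, inexpensive improvement to the analysis. It is not evidence that an imbalance exists.

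**What to change.** In section 10.1:

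1. Define the day-75 FSIGT comparison as the cohort effect adjusted for first-infusion intraportal IEq/kg, net of any auxiliary graft, or as AUC per IEq/kg. The ratio assumes proportionality; the covariate lets the data estimate the slope. State what relative means.
2. Use a method that tolerates zero or near-zero AUC, such as a rank-based analysis. A plain log transform fails there. The Study Definitions excuse graft-failure subjects from day-75 metabolic testing, so count them as zero or worst rank instead of dropping them.
3. Tabulate first-infusion IEq/kg for both cohorts.
4. At 1 and 2 years adjust for first-infusion IEq/kg only, and report cumulative IEq/kg descriptively.
5. Treat any dose-adjusted model of day-75 independence as a supportive, penalised sensitivity analysis. There are only about 0.167 × 24 = 4 control events.

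The cost is analysis wording and one degree of freedom for the covariate (none for the ratio). Per-infusion IEq/kg must also be obtained from the CIT-06 data, and the documents do not confirm that it is available.

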4.1.1 Primary Endpoints

Primary Clinical Endpoint

The proportion of GLASSIA versus control CIT-06 subjects achieving insulin independence at day 75 after the first infusion of single donor islets.

4.1.2 Secondary Endpoints

Key Secondary Endpoint

Insulin independence

- The proportion of GLASSIA treated versus control CIT-06 subjects who are insulin independent after 1 or more islet infusions at:
 - 1 year after the first islet infusion
 - 1 year after the last islet infusion
 - 2 years after the first islet infusion
 - 2 years after the last islet infusion

Other Secondary Endpoints

Insulin Utilization

- The proportion of GLASSIA treated versus control CIT-06 subjects who are insulin independent after 1 or more islet infusions at:
 - 1 year after the first islet infusion
 - 1 year after the last islet infusion
 - 2 years after the first islet infusion
 - 2 years after the last islet infusion
- Percent change from baseline insulin requirement comparing GLASSIA treated versus control CIT-06 subjects at Day 75, 1 year and 2 years following the first and last islet transplant(s)

Islet Mass

The relative functional engrafted islet mass comparing GLASSIA treated versus control CIT-06 subjects using FSIGT testing at:

- Day 75 after the first islet transplant
- 1 year after the first islet transplant
- 2 years after the first islet transplant
- Correlation of markers of early islet loss as assessed by the rapid release of thrombin-anti thrombin complexes (TAT), C3 and c-peptide, and insulin specific DNA with FSIGT and clinical markers of islet function (HbA1c, insulin independence rates, duration of islet function and insulin independence)
- The proportion of GLASSIA treated versus CIT-06 control subjects with both an HbA1c ≤ 6.5% AND an absence of severe hypoglycemic events:
 - From Day 28 to Day 365 after the first islet transplant
 - From Day 28 to Day 730 after the first islet transplant.
- The proportion of GLASSIA treated versus control subjects with both an HbA1c < 7.0% AND free of severe hypoglycemic events:
 - From Day 28 to Day 365 after the first islet transplant.
 - From Day 28 to Day 730 after the first islet transplant
- The proportion of GLASSIA treated versus control CIT-06 subjects A reduction in HbA1c of 1 point AND an absence of severe hypoglycemia from:
 - From Day 28 to Day 365 after the first islet transplant
 - From Day 28 to Day 730 after the first islet transplant
- Number of severe hypoglycemic events comparing GLASSIA treated versus control CIT-06

subjects at 1 year and 2 years following the *first* and *last* islet transplant(s)

- HbA1c comparing GLASSIA treated versus control CIT-06 subjects at 1 year and 2 years following the *first* and *last* islet transplant(s)

Glycemic Control

- The change in Clarke score from baseline in GLASSIA treated versus control CIT-06 subjects at:
 - 1 year after the first islet transplant.
 - 2 Years after the first islet transplant
- β -score comparing GLASSIA treated versus control CIT-06 subjects at 1 year and 2 years following the *first* and *last* islet transplant(s)
- Glucose variability and hypoglycemia duration derived from the CGMS comparing GLASSIA treated versus control CIT-06 subjects at 1 year and 2 years following the first and last islet transplant(s)
- Basal (fasting) and 90-min glucose and c-peptide derived from the mixed-meal tolerance test (MMTT) comparing GLASSIA treated versus control CIT-06 subjects at 1 year and 2 years following the first and last islet transplant(s)
- MAGE comparing GLASSIA treated versus control CIT-06 subjects at 1 year and 2 years following the first and last islet transplant(s)
- Glycemic lability index (LI) comparing GLASSIA treated versus CIT-06 control subjects at 1 year and 2 years following the first and last islet transplant(s)
- Ryan hypoglycemia severity (HYPO) Score comparing GLASSIA treated versus control CIT-06 subjects at 1 year and 2 years following the first and last islet transplant(s)
- C-peptide: (glucose· creatinine) ratio (CPGCR) comparing GLASSIA treated versus control CIT-06 subjects at 1 year and 2 years following the first and last islet transplant(s)
- Rate of favorable outcome at each center preparing islets (rate of subjects with HbA1c \leq 6.5% and absence of severe hypoglycemic events from Day 28 to Day 730, or reduction in HbA1c of 1 point and absence of severe hypoglycemia from Day 28 to Day 730).

Repeat Transplants

- The proportion of subjects receiving a second islet transplant comparing GLASSIA treated versus control CIT-06 subjects at 1 year and 2 years following the first and last islet transplant(s)
- The proportion of subjects receiving a third islet transplant comparing GLASSIA treated versus control CIT-06 subjects at 1 year and 2 years following the first and last islet transplant(s)

Other Efficacy Endpoints

- Cardiovascular events [death, cerebrovascular accident (CVA), myocardial infarction (MI)] and changes in atherogenic profile for GLASSIA treated versus control subjects at 1 year and 2 years following the first and last islet transplant(s)
- Renal impact measures including renal allograft survival and function measured by glomerular filtration rate (GFR), serum creatinine (SCr) and urinary albumin creatinine ratio comparing

GLASSIA treated versus control subjects at 1 year and 2 years following the first and last islet transplant(s)

Exploratory Mechanistic Endpoints

- Assessment of the effect of AAT on serum cytokines released in the early post transplant period (1 month) comparing GLASSIA versus control subjects from CIT-06
- Assessment of the effect of AAT on the inflammatory gene transcriptional profile of PBL at day 14 and 75 comparing pre-and post transplant samples
- Correlation of reaching target AAT levels with metabolic outcomes
- Histological survival of subcutaneous islets in subcutaneous auxiliary graft and correlation with overall graft survival

